8.5 Interim Monitoring Guidelines

Regular reports of safety will be compiled and presented to the DSMB at six months and then yearly; there are no planned formal interim analyses of efficacy using either upper or lower boundary or other methods. Our reason for this choice is based on the speed of accrual relative to the sample size and length of follow-up. An interim analysis which included enough subjects to provide credible data on early stopping for benefit would have to occur so late in recruitment so as to have little or no effect on trial conduct. Between meetings of the DSMB, information regarding issues deemed critical to the trial or participants' safety will be provided to the Chair of the DSMB by the PI. As this is a Phase II study with multiple secondary end points and the first study of letrozole for this indication, there will be no formal stopping rules for futility.

8.6 Protocol Violations

Serious protocol violations such as discontinuation of experimental treatment unrelated to adverse events (AEs) will be carefully recorded and regularly reviewed by the Principal Investigator. Remedial changes in procedure will be recommended where feasible to reduce the incidence of such violations. The causes and circumstances of all violations will be documented

where known for purposes of future secondary analyses and interpretation. Because all primary analyses will be intent-to-treat, it is essential that violations be kept to a minimum, especially where it is possible to influence their rate of occurrence.

8.7 Safety Analysis

All patients will be assessed for toxicity and included in the safety analysis. This analysis will include summaries of the incidence and grade of toxicities. Safety interim analyses will be performed and reported at each continuing review. Patients will be evaluated for SAEs.

9 Participant Safety, Adverse Events, and Confidentiality

9.1 Consent

Consent will be obtained for enrollment from participants. For each consent process, study personnel will discuss the details of the study, the risks and benefits, and the subject's rights and responsibilities if they choose to participate in the trial and their right to refuse to participate. It will be made clear that their clinical care will not be affected by their decision.

Each subject will have ample time and opportunity to ask questions and will be informed about the right to withdraw from the study at any time without any disadvantage and without having to provide reasons for this decision.

Only if the subject voluntarily agrees to sign the ICF and has done so, may he/she enter the study. Additionally, the investigator or assigned study staff will personally sign and date the form. The subject will receive a copy of the signed and dated form.

The signed informed consent statement is to remain in the investigator site file or, if locally required, in the patient's note/file of the medical institution.

The ICF and any other written information provided to subjects will be revised whenever important new information becomes available that may be relevant to the subject's consent, or there is an amendment to the protocol that necessitates a change to the content of the subject information and / or the written ICF. The investigator will inform the subject of changes in a timely manner and will ask the subject to confirm his/her participation in the study by signing the revised ICF. Any revised written ICF and written information must receive the IEC/IRB's approval in advance of use.

9.2 Institutional Review Board Process

Study staff at each site will obtain IRB approval before any study procedures are initiated.

9.3 Safety and Adverse Events

9.3.1 Definitions

Unanticipated Problem (UP): Any incident, experience, or outcome that meets all of the following criteria:

- unexpected (in terms of nature, severity, or frequency) given a) the research procedures that are described in the protocol-related documents, such as the IRB-approved research protocol, informed consent document, or investigators brochure; and b) the characteristics of the subject population being studied;

- related or possibly related to participation in the research (Possibly related to participation in the research means there is a reasonable possibility that the AE, experience, or outcome may have been caused by the procedures involved in the research.); and
- suggests that the research places subjects or others at a greater risk of harm (including physical, psychological, economic, or social harm) than was previously known or recognized.

Adverse event (AE): Any symptom, sign, illness or experience that develops or worsens in severity during the course of the study. Intercurrent illnesses or injuries should be regarded as AEs. Abnormal results of diagnostic procedures are considered to be AEs if the abnormality:

- results in study withdrawal
- is associated with a serious AE
- is associated with clinical signs or symptoms
- leads to additional treatment or to further diagnostic tests
- is considered by the investigator to be of clinical significance

Serious adverse event (SAE): Adverse events are classified as serious or non-serious. A serious adverse event is any AE that is:

- fatal
- life-threatening
- requires or prolongs hospital stay
- results in persistent or significant disability or incapacity
- a congenital anomaly or birth defect
- an important medical event

Important medical events are those that may not be immediately life threatening, but are clearly of major clinical significance. They may jeopardize the subject, and may require intervention to prevent one of the other serious outcomes noted above. For example, drug overdose or abuse, a seizure that did not result in in-subject hospitalization or intensive treatment of bronchospasm in an emergency department would typically be considered serious.

All AEs that do not meet any of the criteria for serious should be regarded as non-serious AEs.

Suspected adverse reaction: Any adverse event for which there is a reasonable possibility that the drug/investigational product caused the adverse event. For reporting purposes, "reasonable possibility" means there is evidence to suggest a causal relationship between the drug/investigational product and the adverse event.

Internal adverse event: Adverse events experienced by subjects enrolled by the investigator(s) at their own Field Center.

External adverse event: Adverse events experienced by subjects enrolled by investigators at other Field Centers in the clinical trial.

9.3.2 Classifying Adverse Events

Severity

The intensity of the AE is classified according to the CTCAEv4.0. Grade refers to the severity (intensity) of the AE:

- **CTCAEv4 Grade 1:** mild; asymptomatic or mild symptoms; clinical or diagnostic observations only; intervention is not indicated.
- **CTCAEv4 Grade 2:** moderate; minimal, local, or non-invasive intervention is indicated; limiting to age-appropriate instrumental activities of daily living (ADL; instrumental ADL refers to preparing meals, shopping for groceries or clothes, using the telephone, managing money, etc.).
- **CTCAEv4 Grade 3:** severe or medically significant but not immediately life threatening; hospitalization or prolongation of hospitalization is indicated; disabling; limiting to self-care ADL (self-care ADL refers to bathing, dressing and undressing, feeding self, using the toilet, taking medications, and not bedridden).
- **CTCAEv4 Grade 4:** life-threatening consequences; urgent intervention is indicated.
- **CTCAEv4 Grade 5:** death due to an AE.

Expectedness

AEs must be assessed as to whether they were expected to occur or were unexpected, meaning not anticipated based on current knowledge found in the protocol, investigator brochure, product insert, or label.

Expected: an AE known to be associated with the intervention or condition under study.

Unexpected: an AE for which the nature or severity is not consistent with information about the condition under study or intervention in the protocol, consent form, product brochure, or investigator brochure.

OHRP defines an **unexpected AE** as any AE occurring in one or more subjects participating in a research protocol, the nature, severity, or frequency of which is **not** consistent with either:

- 1) the known or foreseeable risk of AEs associated with the procedures involved in the research that are described in a) the protocol-related documents, such as the IRB-approved research protocol, any applicable investigator brochure, and the current IRB-approved informed consent document, and b) other relevant sources of information, such as product labeling and package inserts; or
- 2) the expected natural progression of any underlying disease, disorder, or condition of the subject(s) experiencing the AE and the subject's predisposing risk factor profile for the AE.

Relatedness

- **Definite:** the AE is clearly related to the research procedures
- **Probably:** the AE is likely related to the research procedures
- **Possible:** the AE may be related to the research procedures
- **Unlikely:** the AE is doubtfully related to the research procedures
- **Unrelated:** the AE is clearly not related to the research procedures

For each identified AE, an entry on the AE form will be completed. Reporting procedures should be started immediately upon learning of a SAE.

9.3.3 Interpretation of Definitions

AE Reporting Period

The study period during which AEs must be reported is normally defined as the period from the initiation of any study procedures to the end of the study treatment follow-up. For this study, the end of study treatment follow-up is Week 14.

Pre-existing Condition

A pre-existing condition is one that is present at the start of the study. A pre-existing condition should be recorded as an AE if the frequency, intensity, or the character of the condition worsens during the study period.

General Physical Examination Findings

At screening, any clinically significant abnormality should be recorded as a pre-existing condition. At the end of the study, any new clinically significant findings/abnormalities that meet the definition of an AE must also be recorded and documented as an AE.

Post-Study AE

All unresolved AEs considered possibly, probably or definitely related to the study drug should be followed by the investigator until the events are resolved, the subject is lost to follow-up, or the AE is otherwise explained. At the last scheduled visit, the investigator should instruct each subject to report any subsequent event(s) that the subject, or the subject's personal physician, believes might reasonably be related to participation in this study. The investigator should notify the study sponsor of any death or AE occurring at any time after a subject has discontinued or terminated study participation that may reasonably be related to this study. The sponsor should also be notified if the investigator should become aware of the development of cancer or of a congenital anomaly in a subsequently conceived offspring of a subject that has participated in this study.

Abnormal Laboratory Values

A clinical laboratory abnormality should be documented as an AE if any one of the following conditions is met:

- The laboratory abnormality is considered clinically significant by the local PI and is not otherwise refuted by a repeat test to confirm the abnormality
- The abnormality suggests a disease and/or organ toxicity
- The abnormality is of a degree that requires active management; e.g. change of dose, discontinuation of the drug, more frequent follow-up assessments, further diagnostic investigation, etc.

Hospitalization, Prolonged Hospitalization or Surgery

Any AE that results in hospitalization or prolonged hospitalization should be documented and reported as a serious AE unless specifically instructed otherwise in this protocol. Any condition responsible for surgery should be documented as an AE if the condition meets the criteria for an AE.

Neither the condition, hospitalization, prolonged hospitalization, nor surgery are reported as an AE in the following circumstances:

- Hospitalization or prolonged hospitalization for diagnostic or elective surgical procedures for a pre-existing condition. Surgery should not be reported as an outcome of an AE if the purpose of the surgery was elective or diagnostic and the outcome was uneventful.
- Hospitalization or prolonged hospitalization for therapy of the target disease of the study, unless it is a worsening or increase in frequency of hospital admissions as judged by the clinical investigator.

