3.3 Duration of Participation

Subjects will participate for 6 months.

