5.2 Treatment Regimen

Subjects will take 2.5 mg of Letrozole or an identical placebo by mouth daily for 6 months.

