5.4 Preparation and Administration of Study Drug

Letrozole and placebo tablets will be over-encapsulated by the Research Pharmacy both at the Mayo Clinic and at the University of California, San Francisco. At the Research Pharmacy, capsules will be packaged into identical bottles with a liner, cotton, and childproof cap. Bottles will be labeled to meet state and FDA requirements. There will be two visits during which the drug will be administered. At the (Baseline), subjects will receive a 3-month supply; and at their 3 month, (Month 3) subjects will receive a 3-month supply of drug.

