6.3 Visit 4: 6 Month Visit (+/- 30 day window)

The research coordinator will remind the subject to avoid heavy exercise for 12 hours prior to the study visit. The coordinator will also request that the subject refrain from smoking for 12 hours prior to the study visit.

The subject will arrive at the study site outpatient clinic. The following procedures will be performed:

- Labs/Phlebotomy: complete blood count with differential, including hemoglobin, hematocrit, and platelet count, complete metabolic panel, and coagulation studies, lipid panel, estradiol, progesterone, testosterone, sample for storage for future studies; stored samples will only apply to the 10 Mayo participants.
- Arterial blood gas (while seated while breathing room air)
- Technetium macroaggregated albumin perfusion scan

- Review of medical history
- Review current medications
- Vital signs
- Contrast echocardiogram
- Physical exam
- Modified Medical Research Council Dyspnea Scale assessment
- SF-36 questionnaire assessment
- 6 minute walk distance with Borg Score

Blood samples for study assays will be processed and/or banked.

After all these studies have been completed, the investigator or research coordinator will take an interim medical history and perform a physical examination including vitals, review current medications, and complete the mMRC Dyspnea Scale assessment.

The research coordinator will thank the subject for his or her participation. The coordinator will contact the clinician 24 hours after the study visit to discuss the clinical lab results.

Test	Baseline	1 month	3 months	6 months
History	X	X	X	X
Modified Medical Research Council (mMRC) Dyspnea Scale	X	X	X	X
Assessment of adverse effects-		X	X	X
Assessment of compliance		X	X	X
Physical examination, including vital signs	X	X**	X	X
Room air arterial blood gas in seated position	X		X	X
Laboratory Data*	X		X	X
SF-36	X			X
Contrast-enhanced echocardiogram	X			X
Technetium macroaggregated albumin perfusion scan	X			X
6 minute walk distance with Borg Score at baseline and completion	X			X
Complete pulmonary function tests if not performed within 3 years (spirometry, lung volumes and diffusion capacity)	X			
DEXA Scan	X			
Dispense study medication	X		X	

* Laboratory data to include complete blood count, complete metabolic panel, lipid panel, PT/INR, estradiol, progesterone and testosterone levels and stored samples for future analysis.

** If in-clinic visit

7 Assessment of Efficacy and Outcome Measures

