- Date and time of AE resolution, if available
- Concomitant medications that the participant was taking for an underlying medical condition or disease and the therapeutic agents used for the treatment of the adverse event
- Clinical assessment of participant conducted at time of SAE/AE
- Results of any laboratory and/or diagnostic procedures, and treatment
- Follow-up plan
- Outcome
- Autopsy findings (if appropriate)

The participating Investigator will provide details about the AE to the CCC as they become available. If additional information cannot be obtained for whatever reason, this will be documented. The participating Investigator should inform the CCC when no other information is expected. The participating Investigator should provide the CCC with a logical, complete, and accurate narrative description of the SAE based upon the above information. The participating Investigator should promptly determine an assessment of causality.

The participating Investigator should communicate to the CCC if the IRB requires revisions to the informed consent form or other measures.

The CCC will determine if any corrective actions should be initiated as a result of any known specific or collective SAE/AE(s) and inform all participating Investigators of the corrective action (e.g., revision of informed consent form, protocol, CRF).

The participating Investigator/designee should keep originals or photocopies of all relevant documentation, including facsimile confirmations, and file them in the participant's file.

All participating Investigators should ensure that their sites report all routine AE(s) as part of the periodic or annual reporting requirements to the IRB of record.

The CCC and any participating Investigator should file copies of all correspondence with the IRB in the appropriate section of the Regulatory Master File or site study file.

Other Reportable events:

The following events are also reportable to the IRB:

- Any adverse experience that, even without detailed analysis, represents an unexpected SAE that is rare in the absence of drug exposure (such as agranulocytosis, hepatic necrosis).
- Any AE that would cause a modification to the investigators brochure, protocol or ICF, or would prompt other action by the IRB to assure protection of human subjects.
- Information that indicates a change to the risks or potential benefits of the research, in terms of severity or frequency. For example:

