10.1 Personnel Training

Prior to randomization of the first subject in the study protocol, the PI will ensure that the staff has completed appropriate training and that all documentation including IRB approval is completed and available. The purpose of training is to ensure that study personnel are carrying out the protocol in a consistent way and adhering to good clinical practice guidelines. Staff will have current Human Subjects Training Certification on file. Before enrollment begins, study coordinators and research assistants who will perform the outcome assessments will be trained in all procedures, including completion of the web-based database.

The PI and research staff will constitute the first line of monitoring of the safety of the human participants. Surveillance for AEs will consist of questioning subjects about potential AEs at every study contact, having subjects report any AE to the study team, and having subjects undergo vital sign checks and physical exams during each study visit. Laboratory values will be performed at selected visits and checked.

All study personnel are required to read the consent form and the protocol.

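### Section 9.3.3 closes mandatory adverse event reporting at Week 14, although study drug, participation and adverse event assessment run to 6 months

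*Combined protocol and SAP*

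**What the plan says.** Section 9.3.3 (AE Reporting Period) runs mandatory reporting from the first study procedure to the end of study treatment follow-up, and gives the value for this trial: "For this study, the end of study treatment follow-up is Week 14".

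The treatment and visit plan is longer:

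- Section 5.2: "Subjects will take 2.5 mg of Letrozole or an identical placebo by mouth daily for 6 months".
- Section 3.3: "Subjects will participate for 6 months".
- Section 5.4, on the second dispensing: "at their 3 month, (Month 3) subjects will receive a 3-month supply of drug".
- The schedule table after section 6.3 has a row "Assessment of adverse effects", marked at 1, 3 and 6 months. The itemised list for the 1-month visit (section 6.1.2) names this assessment; the lists for the 3-month and 6-month visits (sections 6.2 and 6.3) do not.

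Other sections set adverse event duties without a Week 14 limit:

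- Section 9.3.2: "For each identified AE, an entry on the AE form will be completed".
- Section 9.3.4 tells investigators to "ensure that their sites report all routine AE(s) as part of the periodic or annual reporting requirements to the IRB of record".
- Section 10.1: "Surveillance for AEs will consist of questioning subjects about potential AEs at every study contact".

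**The concern.** The protocol gives two answers to a simple question: must an adverse event in, say, month 5 be reported? Section 9.3.3, read literally, says the mandatory period has closed. The schedule table and sections 9.3.2, 9.3.4 and 10.1 imply that it has not.

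Safety and side effects are a secondary endpoint (sections 3.5 and 7.2). The incidence and grade summaries in sections 8.4.3 and 8.7, and the safety reports to the DSMB and IRB, rely on both sites applying one rule. If one site stops routine reporting at Week 14 and the other continues to month 6, the pooled rates mix two observation periods. The events most exposed are expected or non-serious ones, such as the arthralgia and edema listed in section 1.4, and these make up much of a tolerability profile.

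**Working it through.** **Can Week 14 be derived from the schedule?** Week 14 is 14 × 7 = 98 days. With a month of 365.25/12 = 30.4 days, that is 98/30.4 = 3.2 months. The scheduled points are:

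| Point | Day | Week |
|---|---|---|
| Month 3, nominal | 91.3 | 13.0 |
| Month 3, window ± 30 days | 61.3 to 121.3 | 8.8 to 17.3 |
| Month 6, nominal | 182.6 | 26.1 |
| Month 6, window ± 30 days | 152.6 to 212.6 | 21.8 to 30.4 |

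No visit is set at Week 14, and even the earliest permitted 6-month visit comes almost 8 weeks later. Day 98 lies inside the month-3 window, so a month-3 visit can fall on either side of the cut-off.

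**Share of planned treatment after the cut-off.** The formula is (T − 98)/T, where T is the planned treatment length in days. Counting from first dose is an assumption.

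- 26 weeks: (182 − 98)/182 = 84/182 = 46.2%
- 6 × 30.4 days: 84.6/182.6 = 46.3%
- 6 × 30 days: 82/180 = 45.6%
- 6 × 28 days: 70/168 = 41.7%

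If T is instead the day of the 6-month visit, the window gives 54.6/152.6 = 36% to 114.6/212.6 = 54%.

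**Origin.** Section 9.3.3 starts the period at the first study procedure, and section 6.1.1 allows up to 60 days from consent to baseline. If Week 14 were counted from consent and the full 60 days were used, it would fall on day 98 − 60 = 38 after baseline, leaving (182 − 38)/182 = 79% of treatment uncovered. An earlier origin only enlarges the gap.

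**Share of the second supply after the cut-off**, dispensed at nominal month 3 and counted from first dose: 84/91 = 92.3%. The other month conventions give 84.6/91.3 = 92.7%, 82/90 = 91.1% and 70/84 = 83.3%.

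**Do other clauses close the gap?**

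| Clause | What it covers after Week 14 | What it leaves open |
|---|---|---|
| 9.3.3, Post-Study AE (notice to the sponsor) | Deaths and events reasonably related to the study, once a patient has discontinued or ended participation | Patients still in the study |
| 9.3.4, expedited IRB report | Events that are unexpected, related and suggest greater risk | Expected or unrelated events |
| 9.3.4, report to the coordinating center | Serious and unexpected events, related or not | Expected or non-serious events |
| 9.3.2, 9.3.4 (routine AEs), 10.1 | All events, no time limit stated | No end date that overrides Week 14 |

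The first three rows miss an expected or non-serious event in a patient still on study. The last row covers it, but by contradicting section 9.3.3, not by settling which text governs.

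**Scale in the summaries.** With 10 patients per arm, one patient counted or not counted moves that arm's incidence by 1/10 = 10 percentage points. This applies only if the same event had not already been counted for that patient before Week 14.

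**The case against.** The best case on the other side is that the practical risk is small. The working text points to capture through month 6: the schedule table, a form entry for every event, and questions at every contact. Serious unexpected events go to the coordinating center at any time. Section 10.1 requires training so that staff apply the protocol consistently, and section 10.2 provides on-site audits that review serious events. Section 9.4 refers to sorafenib, which is not a study drug here, so Week 14 may likewise be carried-over text that nobody intends to follow; that is inference. Because the trial is double-blind, a site's cut-off should apply to both arms alike, so the comparison between arms suffers less than the absolute rates.

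Much of this stands. It supports saying that sites could differ, not that data will be lost, and it limits the effect on the treatment comparison. It does not remove the contradiction. Training teaches the protocol as written, and the protocol is inconsistent. The audit text names serious events, not routine ones. Section 4.4 describes blocked randomization without stating stratification by site, so a site difference need not cancel exactly between arms.

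A second objection is that the 6-month visit may take place up to 30 days early, so ending the period there could precede the planned last dose. The point is fair but minor: that visit is the last scheduled contact, and the post-study clause in section 9.3.3 covers related events after it.

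**Conclusion.** The concern holds. The Week 14 end of mandatory reporting is wrong as written: it cannot be squared with 6 months of drug, 6 months of participation, or the month-6 assessment. Counted from first dose, about 12 of 26 planned treatment weeks (46%; 42% to 46% across month conventions) lie outside the stated period. Extending to either end of the 6-month visit window gives 36% to 54%, and counting from consent could raise the share to 79%.

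The consequence is possible uneven reporting of expected or non-serious events between two sites. The primary endpoint is untouched, and loss of late safety data is not certain because other sections still call for capture. The point should be fixed, but it does not threaten the trial's main result.

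**What to change.** Reconcile section 9.3.3 with sections 3.3 and 5.2 and the schedule table. Replace Week 14 with the 6-month visit, or the last study contact for a patient who leaves early, as the end of the adverse event reporting period. State the time origin, and state how events are handled if the 6-month visit falls before the last dose.

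As a minor consistency edit, add the adverse effect assessment to the itemised lists in sections 6.2 and 6.3, as the 1-month list already has it, so that the visit text matches the table.

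The cost is an amendment of a sentence or two plus two list items. No visit or test is added, because the schedule table already places the assessment at months 3 and 6.

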3.5 Secondary Study Endpoints

- Secondary Endpoints:
 - o Difference in changes in intrapulmonary shunting between letrozole and placebo groups at 6 months
 - o Difference in changes in estradiol, progesterone, testosterone levels between letrozole and placebo groups at 3 months and 6 months
 - o Difference in changes in SF36 scores and mMRC dyspnea scale scores between letrozole and placebo groups at 6 months
 - o Difference in changes in distance walked in six minutes between letrozole and placebo groups at 6 months
 - o Difference in changes in PaO₂ and oxygen saturation by pulse oximetry between letrozole and placebo groups at 3 months and 6 months
 - o To assess the effect of letrozole versus placebo on AaPO₂ at 3 months and 6 months
 - o Safety and side effects associated with letrozole administration in patients with HPS
 - o Change in upright A-a gradient from baseline to 6 month follow-up

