6.2 Visit 3: 3 Month Visit (+/- 30 day window)

The coordinator will request that the subject refrain from smoking for 12 hours prior to the study visit.

The subject will arrive at the study site outpatient clinic. The following procedures will be performed:

- Labs/Phlebotomy: complete blood count with differential, including hemoglobin, hematocrit, and platelet count, complete metabolic panel, and coagulation studies, lipid panel, estradiol, progesterone, testosterone, sample for storage for future studies; stored samples will only apply to the 10 Mayo participants.
- Arterial blood gas (while seated while breathing room air)
- Review of medical history
- Review current medications
- Vital signs
- Physical exam
- Modified Medical Research Council Dyspnea Scale assessment
- Dispense supply of study drug (3 month supply to be given at this visit)
- Reinforce instructions on recording of new medications and dose changes
- Reinforce instructions on bringing the subject's routine and study medications to all visits

Blood samples for study assays will be processed and/or banked.

The investigator or research coordinator will take an interim medical history and perform a physical examination including vitals, review current medications, and complete the mMRC Dyspnea Scale assessment. A pre-packaged 3 month supply of study medication (encapsulated letrozole 2.5 mg or placebo capsules) will be prepared for the subject by the Research Pharmacy. Subjects will again be instructed on the proper administration of the study medication.

Once instruction has been given to the subject and the subject expresses understanding, the research coordinator will thank the subject for their attendance and reinforce compliance with the study medication and protocol. The coordinator will contact the clinician 24 hours after the study visit to discuss the clinical lab results.

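### Section 9.3.3 ends mandatory AE reporting at Week 14, which contradicts 6 months of treatment and a scheduled month-6 safety assessment

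*Combined protocol and SAP*

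**What the plan says.** Section 9.3.3 defines the AE reporting period as normally "the period from the initiation of any study procedures to the end of the study treatment follow-up" and then gives the value for this trial: "For this study, the end of study treatment follow-up is Week 14".

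The rest of the protocol runs to month 6:

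- Section 5.2: "Subjects will take 2.5 mg of Letrozole or an identical placebo by mouth daily for 6 months". Section 3.3 sets participation at 6 months.
- Section 6.2, headed "Visit 3: 3 Month Visit (+/- 30 day window)", dispenses a second 3-month supply of drug.
- Section 6.3, headed "Visit 4: 6 Month Visit (+/- 30 day window)", is the last visit. Its schedule table marks AE assessment at months 1, 3 and 6, and laboratory data at baseline, month 3 and month 6. The table note reads: "Laboratory data to include complete blood count, complete metabolic panel, lipid panel, PT/INR, estradiol, progesterone and testosterone levels".
- Section 3.5 lists as a secondary endpoint: "Safety and side effects associated with letrozole administration in patients with HPS".
- Section 8.7 says of the safety analysis: "This analysis will include summaries of the incidence and grade of toxicities". It states no time window and does not refer to 9.3.3.

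**The concern.** The only explicit end date for required AE reporting falls roughly halfway through treatment, about a week after the target date for dispensing the second half of the drug supply. No visit has Week 14 as its target, although the month-3 window includes it.

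Safety is a stated endpoint, and section 8.5 calls this the first study of letrozole for this indication. Section 1.3 gives 2 to 6 weeks to reach steady state, so all treatment after Week 14 is at full exposure. One site could follow the reporting rule and the other the schedule, and AE ascertainment would then differ between them. An analyst could also produce two defensible toxicity tables from the same records. With 10 subjects per arm, a few events change the picture.

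**Working it through.** Week 14 is a stated time point with no calculation behind it, so there is no figure of the plan's to reproduce. The sample size and power in 8.2 do not enter.

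**Inputs.** End of required reporting: Week 14 (9.3.3). Treatment: 6 months (5.2). Visit windows: plus or minus 30 days (6.2, 6.3). Subjects: 20, with 10 per arm (Study Summary). Steady state: 2 to 6 weeks (1.3). Assumptions: one month is 365.25/12 = 30.44 days, and weeks are counted from the baseline visit, when subjects are randomized and given drug. Counting from an earlier study procedure would put Week 14 sooner in treatment.

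**Treatment after Week 14**

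- 6 months = 6 × 30.44 = 182.6 days = 26.09 weeks. Week 14 = day 98.
- Weeks after the end date: 26.09 − 14 = 12.09. Share: 12.09/26.09 = 46%.
- If all 20 subjects complete: 20 × 12.09 = 242 of 20 × 26.09 = 522 subject-weeks.
- Share of steady-state time: 12.09/(26.09 − 2) = 50% to 12.09/(26.09 − 6) = 60%.

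**Visits**

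- Month 6: days 152.6 to 212.6, or weeks 21.8 to 30.4. The earliest permitted visit is 21.8 − 14 = 7.8 weeks after the end date, so every in-window month-6 visit and laboratory panel falls outside. Over this window the uncovered share runs from 7.8/21.8 = 36% to 16.4/30.4 = 54%.
- Month 3: target day 91.3, window to day 121.3. A visit 7 or more days late also falls after day 98.

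**Could Week 14 mean 14 weeks after the last dose?** No. Participation is 6 months and no later visit exists.

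**Conditional illustration.** Suppose Week 14 is enforced in both recording and analysis, and the event hazard is constant. Incidence by Week 14 is then 1 − (1 − p)^(14/26.09), where p is the 6-month incidence. The values of p are assumed.

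| p | By Week 14 | Expected cases in 10, month 6 / Week 14 |
|---|---|---|
| 10% | 5.5% | 1.0 / 0.55 |
| 30% | 17.4% | 3.0 / 1.74 |
| 50% | 31.1% | 5.0 / 3.11 |

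That is 38% to 45% fewer cases. For a 10% event, the chance of seeing none in 10 subjects rises from 0.90^10 = 35% to 0.945^10 = 57%. Early-onset events would lose less and late-onset events more. If the schedule is followed, nothing is lost.

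**The case against.** The strongest reply is that other provisions already carry AE recording to month 6. Section 9.3.1 defines an AE over the whole course of the study. Section 9.3.2 requires a form entry for every AE identified, with no time limit. Section 10.1 has subjects asked about AEs at each contact, and the 6.3 table marks AE assessment at month 6. The laboratory rule in 9.3.3 has no end date of its own, and the same section asks for new clinically significant findings at the end of the study to be recorded, though under its physical examination heading. Section 8.7 does not cite Week 14, and a period of mandatory reporting does not tell an analyst to discard later events.

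Most of this stands. It makes it likely that many late events would be recorded. A reader might infer that the safety table will omit almost half of the exposure, or every month-6 laboratory abnormality. The documents do not support that, because both outcomes require sites or analysts to enforce Week 14 against these provisions.

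The reply does not remove the conflict. None of these provisions corrects the date. The word normally in 9.3.3 does not help either, since the next sentence gives the value for this study. The procedure list for the 1-month visit names AE assessment, but the lists for the 3- and 6-month visits do not, so the month-6 assessment rests on a table row and the general statement in 10.1.

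The reporting routes in 9.3.4 are also narrower than they look. Reporting to the institutional review board at any time covers events that are unexpected, related and suggestive of greater risk. The route to the coordinating center covers serious unexpected events. Toxicities already listed in 1.4, such as hypercholesterolemia (52.3%), arthralgia (8% to 48.2%) and fracture (5.9% to 14.7%), are expected, so neither route is built to catch them.

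**Conclusion.** The contradiction is certain. Section 9.3.3 states an end date that cannot be right for a 6-month treatment period, and 12.1 of 26.1 weeks (46%) lie beyond it, along with all in-window month-6 visits. What follows for the data is not certain: two rules are in force, and the exposed events are mainly expected or non-serious AEs. The case-loss figures above hold only if Week 14 is enforced, and they rest on assumed incidences and a constant hazard. They are not a forecast.

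A reader might also infer from the mention of sorafenib in 9.4, a drug not used in this trial, that Week 14 was carried over from another protocol. That is plausible but unproven, and the point does not depend on it. The primary endpoint and its power are not affected. The correction should be made because the rule is wrong as written and cheap to put right.

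**What to change.** 1. In 9.3.3, replace Week 14 with: *the Month 6 visit, or 6 months (+30 days) after randomization if that visit is not attended*. State that this also applies to subjects who stop study drug early and remain in follow-up under 8.4.5. The fallback gives an end date for subjects who miss the visit and matches the upper limit of the 6.3 window.
2. In 8.7, add: *The toxicity summary, by arm, covers AEs over the reporting period defined in 9.3.3.* This keeps the existing start at the first study procedure. Treatment-emergent events, counted from first dose, may be shown separately.

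The cost is one date and one sentence. No visit, test or sample-size change is needed, because the month-6 AE assessment and laboratory draw are already scheduled. The downside is a chart check for weeks 15-26 in earlier subjects if any site has already stopped recording at Week 14.
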